# BRECLIM

### **Breast Cancer Liver Metastasis**

## A multicentre randomized clinical trial investigating local treatment for breast cancer liver metastasis

Protocol Version	2020-09-14				
	ClinicalTrials.gov Identifier: NCT04079049				
Trial registration	Cancer studies in Sweden (cancercentrum.se) #88154				
Trial funding	Swedish Breast Cancer Association				
Trial funding	Swedish Research Council				
Methodology:	Multiple Center Randomized Clinical Trial				
Study Duration	The planned duration of study participation for an individual				
Study Duration:	subject from inclusion to follow-up are at least 3 years				
	Norrlands University Hospital Umeå				
	Sahlgrenska University Hospital Gothenburg				
Study Centers:	Skane University Hospital Lund				
Study Centers.	Akademiska University hospital Uppsala				
	University Hospital of Linkoping				
	Karolinska University Hospital Huddinge				
Primary Investigator:	[name] (Umeå)				
	[name] (Umeå)				
	[name] (Umeå)				
Study coordinating group	[name] (Umeå)				
	[name] (Göteborg)				
	[name] (Sunderbyn)				
Statistician	[name] (Umeå)				
Data Management	[name] (Stockholm)				
Project coordinator	[name] and [name] (Umeå)				
Study nurse coordinator	[name] (Umeå)				
	[name] (Umeå)				
	[name] (Gothenburg)				
Local Investigators	[name] (Linköping)				
surgery:	[name] (Uppsala)				
	[name] (Stockholm)				
	[name] (Lund)				
	[name] (Umeå)				
	[name] (Gothenburg)				
Local Investigators	[name] (Linköping)				
oncology:	[name] (Uppsala)				
	[name] (Stockholm)				
	[name] (Lund)				
	Representative for surgery				
Safety committee	Representative for oncology				
	Representative for statistics				
Study monitor	Clinical trial unit Umeå				

	Primary endpoint:				
	1. Time to death from any cause				
	Secondary endpoints:				
	1. Three years survival				
	2. Progression free survival				
Objective(s)/ Outcome(s):	3. Median overall survival				
	4. Breast cancer specific survival				
	5. Overall complications				
	6. Quality of life				
Number of Subjects	7. Prognostic factors				
Number of Subjects:	200 patients, 100 in each arm				
	§ 1-4 liver metastasis amendable to surgery with functional				
	liver remnant volume >30%.				
	§ Signed informed consent				
	§ >18 years old				
Inclusion Criteria:	§ ECOG 0-1				
	§ Breast cancer history				
	§ Breast cancer liver metastasis verified by biopsy				
	§ Patient amendable for liver surgery and pre- and				
	postoperative oncological treatment				
	§ Previous or present non-skeletal extrahepatic disease				
Exclusion Criteria:	§ Pregnancy				
	§ > 4 liver metastases on preoperative or previous				
	examination				
	§ Progression of disease upon oncological treatment				
Study Schedule:	First-Subject-In is planned in 2020				
	Last-Subject-In is planned for 2026				
	Last-Subject out is planned for 2029				
Ethics approval	Sweden. Dnr 2018-116-31M and 2019-05717				
Web	https://www.umu.se/en/research/projects/the-breclim-trial/				

### **Purpose and aims**

Breast cancer is the second most common cancer in Sweden with an incidence of 8000 per year. Even though the majority is cured from the disease it is the cause of death for 1400 patients in Sweden each year (1). Breast cancer is treated by a combination of surgery, radiotherapy, and (neo-) adjuvant treatment including chemotherapy, endocrine and targeted therapies. The role of surgery for distant breast cancer metastasis beyond local lymph nodes remains controversial even though some reports suggest there might be a survival benefit from resection of oligometastases in the liver.

The purpose of this multicentre randomized clinical trial is to evaluate local treatment for breast cancer liver metastases, compared to systemic oncological treatment only. The primary endpoint is time to death from any cause, which will be compared using cox proportional hazard regression. The secondary endpoints are three years survival, progression-free survival, median overall survival, breast cancer specific survival and quality of life. The aim is also to evaluate overall safety and predictive factors for survival during oncological and surgical treatment. The overall purpose is to ameliorate treatment for advanced breast cancer.

### Survey of the field

Most patients with breast cancer liver metastasis (BCLM) receive only medical treatment today. Isolated BCLM are found in at least 5% of patients with advanced breast cancer (3). This equals to about 70 patients per year in Sweden. Only 5 patients were operated for BCLM per year in Sweden 2009-2016, according to the national registry for liver surgery.

A systemic review on liver resection for BCLM summarizes 43 studies with 1686 patients and reports a median overall survival of 36 months and a 3-year survival of 56% (2). Both Swedish and European guidelines conclude that the value of surgical or other local treatment for BCLM is unknown and that a randomized trial is needed (3, 4). Opponents to surgery argue that the published material has a low level of evidence and surgery could interrupt oncological treatment.

Most previous studies are based on results from a single centre. There are only four studies with a control cohort of patients receiving oncological treatment only. In a retrospective casecontrol trial including 102 patients with a maximum of four BCLM who were stable or responded on oncological treatment (5), a multivariate analysis showed 3.04-fold increased risk of death in the oncological group. In contrast, Sadot et al, compared 67 operated patients to 98 patients only receiving medical treatment (6). Despite more positive prognostic factors in the surgical cohort, there was no survival advantage.

We recently conducted a retrospective study on nationwide cohorts from Swedish quality registers (7). We concluded that liver surgery for BCLM in Sweden is safe but rare. The study showed a significantly longer survival among operated patients compared to those who received medical treatment. When adjusting for prognostic factors, there was still a tendency towards a better prognosis after surgery but the result was no longer significant. A randomized trial without selection bias is needed to evaluate if there is a true difference in survival.

### Study design

This is a randomized trial comparing local treatment of liver metastases in addition to oncological treatment versus medical oncological treatment only. A prospective randomized trial is chosen to avoid selection bias. A flowchart describes the schedule (figure 1).

#### Oncological treatment

Participants in both arms receive oncological treatment. Oncological breast cancer treatment is based on the molecular subtype of the tumour and follows established principles according to the national guideline (3). All participants are discussed at multidisciplinary conferences as in general clinical practice to optimize treatment. Chemotherapy is given for two months while hormonal therapy is given for three months. Those who are stable or respond to treatment are randomized to either surgery followed by oncological treatment or oncological treatment only.

#### Local treatment

Liver surgery or ablation is performed at one of the six study centres, in accordance with the routine at the centre. Radiofrequency ablation or microwave ablation are alternative treatment options to resection for metastases of a maximum size of 2 and 3 cm respectively. Stereotactic body radiotherapy (SBRT) for the liver metastasis can be considered when surgery or radiofrequency-/microwave ablation is not possible. The SBRT should be performed at a radiotherapy department with experience of this treatment. It should be guided by fiducial markers and the dose should be ablative (e.g. 45Gy in 3 fractions).

Participants will be followed by CT every 3 months the first year and every 6 month the following 2 years.

Population:	200 patients with 1-4 BCLM and no extrahepatic disease (except bone metastases) who are stable or respond to oncological treatment.
Intervention:	Local treatment of BCLM by surgical resection, ablation or stereotactic radiotherapy, followed by oncological treatment.
C omparison:	Oncological treatment.
Outcome:	Participants will be followed for at least three years. The primary endpoint is time to death from any cause, which will be compared using cox proportional hazard regression.
Hypothesis:	Local treatment for breast cancer liver metastases improves overall survival, compared to standard medical treatment only.

[figure not shown]

Figure 1.

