## **Research questions**

- Is there a survival benefit of local treatment of BCLM by liver resection, ablation or stereotactic radiotherapy, compared to oncological treatment only? We will primarily compare time to death from any cause and calculate the hazard ratio in each arm, adjusted for known predictive factors. Secondary endpoints are three years overall survival after randomization, median overall survival, progression free survival and breast cancer specific survival.
- 2. What is the complication rate for each treatment and what kind of complications arise? 30-days and 90-days mortality after surgery will be determined and complications will be described and graded by the Clavien-Dindo score. Chemotherapy toxicity will be graded by the CTC 4.03 scale.
- 3. What are the predictive factors for survival after surgical and/or oncological treatment of BCLM? Predictive factors for survival (described on page 4) will be analyzed in a cox proportional hazards model.
- 4. How is quality of life influenced in BCLM patients after surgical treatment compared to oncological treatment? EORTC QLQ-C30 and QLQ-LM21 will be followed at inclusion, and follow up 3, 12 and 24 months after randomization. Quality of life will be analyzed using an ordinal proportional odds regression model.

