### Variables and measures

Variables are collected in electronic case report forms (CRFs) as in figure 1 and table 1. CRF 1 and 2 are divided into section A and B with variables in A related to liver surgery and in B to breast oncology. CRF 3 and 4 is only for those randomized to local treatment.

CRF1		Registration. Ca 15-3. Performance status. Somatic comorbidities.				
		1a BCLM characteristics				
		1b Breast cancer characteristics and. Oncological and surgical breast cancer treatment of prior to inclusion.				
CRF2		2a Liver metastases after oncological treatment. Evaluations of response according to RECIST 1.1 (9).				
		2b Oncological treatment after inclusion.				
		2c. Result of randomization.				
	Only for thos	se randomized to local treatment				
	CRF3	Local treatment.				
	CRF4	Complications (30-day) according to Clavien-Dindo and the CTC 4.03 scale. Pathological anatomical diagnosis of liver metastases including ER, PgR, Her2. Total number of days at hospital.				
CRF5	Follow up 3, 6, 9, 12, 18, 24, 30, 36 months (5a-h). Oncological treatment and grading of complications by the CTC 4.03 scale. Secondary intervention against metastases. Performance score. Quality of life 3, 12 and 24 months.					
CRF6	Recurrence. Progression.					
CRF7	End of study. Vital status.					

For survival analyses, the primary endpoint is time from randomization to death from any cause. Secondary endpoints are three years overall survival, progression free survival, breast cancer specific survival and median overall survival. Disease progression will be evaluated at each radiology control. This analysis cannot be blinded since radiologists can see signs of previous liver resections. Survival will primarily be evaluated in an intention to treat manner and secondary in a per protocol analysis.

To study safety and complications, 30-days and 90-days mortality after surgery will be determined and complications will be described and graded by the Clavien-Dindo score. Chemotherapy toxicity will be graded by the CTC 4.03 scale.

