## Material: Patient selection

Inclusion will start in all six regional cancer centres in Sweden.

Inclusion criteria	
 
§ Signed informed consent
 
§ >18 years old
 
§ ECOG 0-1
 
§ Breast cancer history
 
§ Breast cancer liver metastasis verified by biopsy
 
§ Patient amendable for liver surgery and pre- and postoperative oncological treatment
 
§ 1-4 liver metastasis amendable to surgery with functional liver remnant volume >30%
 

Exclusion criteria	
 
§ Previous or present non-skeletal extrahepatic disease
 
§ > 4 liver metastases on preoperative or previous examination
 
§ Pregnancy
 
§ Progression of disease upon oncological treatment
 

Participants will be randomized by an oncologist at a study centre. Participants will be stratified on study centre. Randomization and stratification will be computer-based and administered upon the study website. The 1:1 allocation of participants into groups will be performed in random blocks, with random block sizes of 2 to 6. The study website will apply the Pheedit system and provide electronic CRFs. Each site coordinator will have access to the website and will be able to include and randomize participants. Non-participants who fulfill inclusion criteria will be registered by date, initials, clinic and date of birth.

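### The protocol does not say when amenability to surgery is judged or how that fits SBRT as a fallback, and the listed forms record the local modality only after allocation in the local arm

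*Protocol*

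**What the plan says.** **Entry.** The synopsis and Material: Patient selection require "1-4 liver metastasis amendable to surgery with functional liver remnant volume" above 30%, and separately "Patient amendable for liver surgery and pre- and postoperative oncological treatment". Neither criterion has an exception. The Population row in Local treatment gives the number of metastases, the absence of extrahepatic disease other than bone, and stable or responding disease, but does not mention resectability.

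**Intervention.** Local treatment says of ablation: "Radiofrequency ablation or microwave ablation are alternative treatment options to resection for metastases of a maximum size of 2 and 3 cm respectively". Of stereotactic radiotherapy it says: "Stereotactic body radiotherapy (SBRT) for the liver metastasis can be considered when surgery or radiofrequency-/microwave ablation is not possible". The Ethics section shows that SBRT came in by amendment. The section on Oncological treatment still names surgery alone: "Those who are stable or respond to treatment are randomized to either surgery followed by oncological treatment or oncological treatment only".

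**Timing.** Table 1 places consent and inclusion at the 1st visit, and randomisation at the 2nd liver surgery MDT with repeat MRI, CT and RECIST assessment. Between them lie two months of chemotherapy or three months of hormonal therapy.

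**Recording.** Variables and measures lists CRF2 as "2a Liver metastases after oncological treatment. Evaluations of response according to RECIST 1.1 (9"), then oncological treatment (2b) and the result of randomisation (2c). Local treatment is the content of CRF3, and "CRF 3 and 4 is only for those randomized to local treatment". Stratification is by centre only.

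**Analysis.** The first research question is "Is there a survival benefit of local treatment of BCLM by liver resection, ablation or stereotactic radiotherapy, compared to oncological treatment only". Survival is analysed primarily by intention to treat and secondarily per protocol.

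**The concern.** SBRT is reserved for patients in whom the other options are not possible, yet entry requires that surgery is possible. Both can be true of one patient only if the judgement is made at different times, and the protocol does not fix those times. One centre may treat amenability as settled at the 1st visit. Another may require it again at the 2nd liver surgery MDT. A third may read the SBRT provision as widening entry. The trial population would then depend on the centre.

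The second issue is information. Who receives SBRT is decided by the patient's condition, so SBRT recipients are likely to differ in prognosis from the average control. If the intended modality is not written down for both arms before allocation, there is no comparable control group for them. An honest pre-allocation intention cannot be reconstructed once the arm is known. This affects any analysis that selects local-arm patients by what they received, including the planned per-protocol analysis.

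**Working it through.** The point rests on the text; the plan gives no figure for it to reproduce. The arithmetic below only shows scale.

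**1. Is there one entry rule?**
- Synopsis and Patient selection: surgery must be possible, with no time point given.
- Local treatment: SBRT may be used when surgery or ablation is not possible, again with no time point.
- Oncological treatment: after the run-in, stable or responding patients are randomised. Amenability is not mentioned.
- Table 1: inclusion and randomisation are two separate visits.

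The texts are compatible if surgery is possible at inclusion and ceases to be possible later. They conflict if amenability must hold throughout and SBRT is nevertheless an option for a randomised patient at the 2nd MDT. The protocol does not choose between these readings.

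**2. Can a control be matched to a modality?**
- CRF1a and CRF2a describe the liver metastases in both arms.
- No listed form records an intended modality. The delivered modality is in CRF3, local arm only, after allocation.
- Ablation: the limits are by size (2 and 3 cm), and lesion size is among the factors to be studied. An ablation-eligible subset might be approximated in both arms, if size is an item in CRF1a or CRF2a.
- SBRT: no comparable marker is evident.

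**3. How far could a split by delivered modality mislead?** (illustration)
Suppose SBRT has the planned effect, a hazard 1/1.9 = 0.53 times that of its own controls, and its recipients have k times the average death hazard. Compared with all controls, the apparent hazard ratio is k/1.9:
- k = 1.25: 0.66
- k = 1.5: 0.79
- k = 2.0: 1.05

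If instead a fraction f of the local arm cannot receive any local treatment, the pooled hazard ratio is roughly 1.9^(1−f): 1.78 for f = 10% and 1.67 for f = 20%. The documents give neither k nor f; both are assumed.

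**4. What could a pre-allocation record support?**
Inputs: hazard ratio 1.9, two-sided 0.05, 190 evaluable patients, 1:1 allocation (Estimated sample size and power; Statistical methods; Patient selection). Deaths are 60%, from the stated 40% three-year survival, with 40% as a sensitivity value. The modality share s is assumed. Deaths d = 190 × s × death proportion. By Schoenfeld, power = Φ(√(d/4) × ln 1.9 − 1.96), with ln 1.9 = 0.642.
- s = 10%, 60% deaths: d = 11.4; √2.85 × 0.642 = 1.08; power about 19%.
- s = 20%, 60% deaths: d = 22.8; √5.7 × 0.642 = 1.53; power about 33%.
- s = 10% and 20%, 40% deaths: d = 7.6 and 15.2; power about 14% and 24%.

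A result for a small modality would therefore be descriptive even with the record in place.

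**The case against.** The strongest reply is that the trial tests a strategy. The Intervention row, the first research question and the Statistical methods pool all local treatment against oncological treatment. Randomisation protects that contrast whatever the mix of modalities. This stands: no survival comparison by modality is planned, and naming three modalities in the research question defines the intervention and does not promise three comparisons.

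Second, SBRT appears in a treatment section that says nothing about enrolment, and a patient can lose resectability between inclusion and treatment. This also stands. A reader might infer a strict contradiction, under which no SBRT patient can ever be eligible. The text does not support that, because the two statements can refer to different times.

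Third, a reader might infer that patients with nothing left to treat are randomised. That would be an inference from silence. Randomisation takes place at a liver surgery MDT with new imaging, and the exclusions for progression and for more than four metastases on preoperative examination show that some criteria operate after the run-in. What remains is that the protocol does not say whether amenability is one of them.

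Fourth, the forms are only summarised, and an item on intended modality could exist in the full CRF. This is a fair limit on the finding, which concerns the forms as listed. Lesion data in both arms also rule out the absolute claim that no modality could be compared with controls.

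**Conclusion.** The point holds in a limited form. The protocol leaves open when amenability to surgery is judged and how that fits SBRT as a fallback, so centres could apply different entry rules. The passages must be reconciled, and which rule applies is for the sponsor to decide. On the forms as listed, controls cannot be identified directly by the modality they would have received. The per-protocol analysis, and any statement by modality, would then select on a variable that arises after randomisation.

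The primary pooled intention-to-treat comparison is not invalidated. The apparent hazard ratios of 0.66 to 1.05, and the dilution to 1.78 or 1.67, might be taken as expected results of this trial. They are not: they follow from assumed values of k and f, and the first set belongs to an analysis that is not planned. The change is still worth making, because it is cheap and the information cannot be recovered without bias after allocation.

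**What to change.** 1. Reconcile the entry criteria (synopsis and Material: Patient selection) with Oncological treatment and Local treatment, including its Population row. State whether amenability is judged at inclusion, at randomisation or both, and how that relates to the SBRT provision. Replace the references to surgery alone where local treatment in general is meant.
2. Add to CRF2a, completed at the 2nd liver surgery MDT for every patient and time-stamped before allocation is released: the lesions present, the intended local modality, and whether local treatment is judged deliverable. This is a record; it should not itself become a new clinical entry rule.
3. Base any result by modality on this field in both arms, not on CRF3, and label it descriptive. Alongside the per-protocol analysis, report a supporting analysis that selects patients in both arms by the pre-allocation field.
4. Do not complete the field retrospectively for patients whose allocation is already known.

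The cost is one extra eCRF entry and a few minutes per patient at a meeting that already takes place, plus a protocol wording amendment with the review that this requires. The gain is limited: a comparable control group for these analyses, without adequate power for a small modality.

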## **Research questions**

- Is there a survival benefit of local treatment of BCLM by liver resection, ablation or stereotactic radiotherapy, compared to oncological treatment only? We will primarily compare time to death from any cause and calculate the hazard ratio in each arm, adjusted for known predictive factors. Secondary endpoints are three years overall survival after randomization, median overall survival, progression free survival and breast cancer specific survival.
- 2. What is the complication rate for each treatment and what kind of complications arise? 30-days and 90-days mortality after surgery will be determined and complications will be described and graded by the Clavien-Dindo score. Chemotherapy toxicity will be graded by the CTC 4.03 scale.
- 3. What are the predictive factors for survival after surgical and/or oncological treatment of BCLM? Predictive factors for survival (described on page 4) will be analyzed in a cox proportional hazards model.
- 4. How is quality of life influenced in BCLM patients after surgical treatment compared to oncological treatment? EORTC QLQ-C30 and QLQ-LM21 will be followed at inclusion, and follow up 3, 12 and 24 months after randomization. Quality of life will be analyzed using an ordinal proportional odds regression model.

